Hypothesis II: CRI and collapsibility index will reliably predict fluid responsive patients with an approximate area under the receiver operating characteristic curve (AUROC) of 0.9 while other indices will have a lower predictive accuracy.

Aim III: Evaluate confounding variables that may influence predictive measures outlined in Aim II.

Hypothesis III: Confounding variables that may decrease the predictive accuracy of indices described in Aim II include spontaneous breathing over the ventilator, minimal blood loss, and hypothermia

4. Materials and Methods:

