2. After positioning the patient for surgery, the CardioQ-EDM device will be placed through the mouth into the esophagus by the PI or Co-investigators (Drs. [name] or [name]) and the aortic Doppler waveform will be confirmed. Additionally, the CipherOx-CRI finger probe will be placed, and a baseline IVC CI will be measured and recorded.
3. Baseline values and measurements (included in **Table 3**) will be recorded. Additionally, the baseline ΔV_{Peak} and CRI will be recorded.
4. A protocolized 10 mg/kg crystalloid fluid bolus will be administered
5. Two minutes after the bolus has completed, repeat EDM and CRI values will be recordings and a repeat abdominal ultrasound to measure the IVC CI will be obtained.
6. If an additional fluid bolus or blood transfusion is administered during the remainder of the procedure, steps 3 and 5 will be repeated.

4.6.1 Demographic Data: Age, weight, height, body mass index (BMI), gender, and ethnicity will be collected from medical records.

4.6.2 Ventilator Data: pressure or volume control, tidal volume (ml/kg) and peak end-expiratory pressure (PEEP), peak inspiratory pressure (PIP), and spontaneously breathing.

4.6.3 CardioQ-EDM Data: Based on a validated internal nomogram derived from the child's age, height, and weight[27], peak velocities will be obtained from the Cardio-EDM monitor.

4.6.4 Fluid Data/Vasopressor Administration: Number, time, type, and volume of fluid/blood administered will be recorded in real time. Vasopressor agent, dose, and time administered will also be reported.

4.6.5 Waveform/Vital Data: As it is currently not possible to extract waveform data from the operating room monitors, we will record data in real time. Values listed below will be reported on an excel spreadsheet.

Parameters to measure:

All parameters will be measured x 3 with 30 seconds between each measurement and averaged

- Systolic blood pressure (measured by arterial line)
- Mean arterial pressure (calculated from arterial line)
- Heart rate
- Pulse pressure variability (measured by arterial line) = acquired from arterial line
- Stroke volume variability – acquired from arterial line
- $\Delta V_{peak} = (V_{Peakmax} - V_{Peakmin}) / [(V_{peakmean}] \times 100$
- Compensatory reserve index – algorithmically generated
- Inferior vena cava collapsibility index = Maximum diameter (expiration) – minimum diameter (inspiration)/maximum diameter (expiration) in M mode

4.7 Data Blinding:

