4.8 Data Analysis

Protocol #: 18-2513

PI: [name]

Version date: 07/01/2019

Univariate comparisons between various measures will be compared between the fluid responder and non-responder groups using t-tests or Fisher's exact test for continuous and categorical measures, respectively. Area under the curve will be calculated for CI and CRI using both simple logistic regression models including no confounders and multiple logistic regression models including confounders. Confounders will be identified for inclusion in the multiple logistic regression models by calculating the univariate association with the gold standard (using a $p < 0.10$ threshold). These adjusted models will be used to verify thresholds for classification using CI and CRI which will then be applied to calculate classification summary measures (e.g., PPV, NPV, sensitivity, and specificity). Data analysis will be performed by a biostatistician funded by the Division of Pediatric Surgery using R and SAS statistical software programs.

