Aim III: Evaluate confounding variables that may influence CRI or collapsibility index

Variable	Scale of Measurement	Data Point Location	Analysis Method
Outcome Variable IVC CI, CRI, PPV, SVV, HR, SBP, MAP AUROC	Interval	Pre-bolus measurements	
Confounding Variables Age Weight BMI Gender Ethnicity Associated syndrome Preoperative Hemoglobin Duration of NPO status Core temperature at time of bolus Paralysis provided (Y/N) Blood transfusion (Y/N) Total blood volume Total Crystalloid Total Colloid Vasopressor requirement Total amount of vasopressor Ventilation Tidal volume PEEP PIP Spontaneous breaths	Interval Interval Interval Dichotomous Ordinal Dichotomous Interval Interval Interval Dichotomous Dichotomous Interval Interval Interval Dichotomous Interval Interval Dichotomous	Demographics Demographics Demographics Demographics Demographics Demographics Demographics Preop results Anesthesia Rec Anesthesia Rec Ventilator Ventilator Ventilator Ventilator	Multivariable Linear Regression

Figure or Table will depend on results found. If neither of the outcome variables are affected by the confounding variables may only report this finding in the text.

Two separate analyses will be performed – one for the 10 ml/kg protocolized bolus provided immediately after induction and one accounting for all boluses provided.

Protocol #: 18-2513

PI: [name]

Version date: 07/01/2019

Reference:

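### Aim III has no blood-loss covariate although Hypothesis III names one, and its fluid, blood and vasopressor totals have no time window, including for the pre-incision bolus

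*Combined protocol and SAP*

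**What the plan says.** Hypothesis III (section 3) concerns "Confounding variables that may decrease the predictive accuracy of indices described in Aim II", and says that these "include spontaneous breathing over the ventilator, minimal blood loss, and hypothermia".

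The Aim III table (section 5) sets the indices, taken from pre-bolus measurements, against a list of confounders. Two of the three named factors are there: "Core temperature at time of bolus" and, at the end of "Tidal volume PEEP PIP Spontaneous breaths", spontaneous breathing. The fluid and drug entries are "Blood transfusion (Y/N) Total blood volume Total Crystalloid Total Colloid Vasopressor requirement Total amount of vasopressor". Core temperature is tied to the bolus; these six entries are tied to no time.

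Below the table the plan adds: "Two separate analyses will be performed – one for the 10 ml/kg protocolized bolus provided immediately after induction", and another for all boluses. The covariate list is the same for both. Section 4.7 and the title of Mock-up Table 1 place the protocolized bolus before incision.

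On data, section 4.6.4 states: "Number, time, type, and volume of fluid/blood administered will be recorded in real time". Vasopressor agent, dose and time are also recorded. Section 4.5 gives blood loss as one input to the anesthesiologist's decision, but sections 4.6.1 to 4.6.5 do not list it as a study variable.

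Section 4.8 states: "Confounders will be identified for inclusion in the multiple logistic regression models by calculating the univariate association with the gold standard", at p<0.10. The adjusted models then verify the CI and CRI thresholds from which PPV, NPV, sensitivity and specificity are calculated.

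**The concern.** There are two gaps. First, one of the three factors in Hypothesis III has no variable in the plan, so the analyst has nothing specified with which to examine it. Section 2 presents validation in children with significant blood loss as the need that the study answers, so the factor is not a side issue.

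Second, a covariate can confound a pre-bolus reading only if it was in place before that reading. A total of blood, colloid, crystalloid or vasopressor with no cut-off may include amounts given afterwards. Those amounts may be consequences of the child's volume state, or of the response that the index is meant to predict. If such a total enters a prediction model, the model draws on information that does not exist when the bolus decision is made. Its AUC, and any threshold verified from it, would then look better than the index can be before the bolus.

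**Working it through.** The plan gives no figure for this point, so there is none to reproduce. The check sets the sections side by side and then sizes the possible effect on an AUC.

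**1. Coverage of Hypothesis III**

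| Factor in Hypothesis III | Aim III table | Items 4.6.1–4.6.5 |
|---|---|---|
| Spontaneous breathing | listed | listed (4.6.2) |
| Hypothermia | core temperature, timed to the bolus | not listed; the table gives the covariate |
| Minimal blood loss | not listed | not listed |

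Two of three factors have a covariate. *Total blood volume* follows the transfusion entry and precedes crystalloid and colloid, so it reads as blood given rather than blood lost, although the table does not define it.

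**2. Timing of the six fluid, blood and vasopressor entries**

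- Protocolized bolus, case totals: the outcome is measured before incision and most of the amounts accrue later. They cannot confound it.
- Protocolized bolus, amounts up to the bolus: most entries would be at or near zero and have little to contribute.
- Later boluses, case totals: each total includes the bolus being predicted and those after it.
- Later boluses, amounts up to the bolus: these are legitimate covariates.

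Only the last combination works as intended, and the table does not say that it is the one meant.

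**3. Could a total pass the 4.8 screen?** Assume 30 infants (section 4.2 lists 30 probes; this is not a stated sample size), 15 responders and 15 non-responders, and a total that differs by δ SD. By the normal approximation, with two-sided p<0.10:

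P(pass) = Φ(δ√(15/2) − 1.645)

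- δ = 0.5: Φ(1.369 − 1.645) = 0.39
- δ = 0.8: Φ(2.191 − 1.645) = 0.71
- δ = 1.0: Φ(2.739 − 1.645) = 0.86

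If the four entries worded as totals were unrelated to response and independent, at least one would still pass with probability 1 − 0.9⁴ = 0.34.

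**4. Effect on the AUC if one enters.** Assume a binormal index and a total independent of it within each group. An index with AUC A has separation d = √2·z(A). Adding the total gives

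AUC = Φ(√(d² + δ²)/√2)

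Worked case: A = 0.70 gives d = 1.414 × 0.524 = 0.742 and d² = 0.55. With δ = 0.5, √(0.55 + 0.25)/√2 = 0.632, and Φ(0.632) = 0.74.

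| Index alone | d² | δ = 0.5 | δ = 0.8 | δ = 1.0 |
|---|---|---|---|---|
| 0.70 | 0.55 | 0.74 | 0.78 | 0.81 |
| 0.80 | 1.42 | 0.82 | 0.84 | 0.86 |
| 0.90 | 3.28 | 0.91 | 0.92 | 0.93 |

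The 0.90 row is the AUC that Hypothesis II expects for CRI and CI. The values of δ are assumptions; the documents give none.

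**The case against.** A reader might infer that the adjusted models use whole-operation totals. The documents do not support that. *Total* is undefined, the records are time-stamped, and section 4.6 has data entered on a form for each bolus, so an amount up to the bolus is an equally possible meaning. Section 4.8 names no covariates and does not point to the Aim III table. Other candidates for its screen appear in the background section, Hypothesis III, sections 4.6.1 and 4.6.2, and Mock-up Table 1. This objection stands: the totals *may* enter, and the plan does not say that they do.

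A reader might also infer that Hypothesis III cannot be answered at all. On this ground that is too broad, since spontaneous breathing and temperature each have a covariate. Whether linear regression of index values can show a loss of predictive accuracy is a separate question, not relied on here.

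Blood loss may be recorded somewhere not seen. Table 3 and the Data Collection Form are cited but are not in the text available, and the Aim III table is broken by extraction. So the claim is that no variable is specified in the visible covariate list and data items, not that no data exist.

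Finally, the AUC effect rests on assumed differences and is only 0.01 to 0.03 at an AUC of 0.90, and section 4.8 also calculates an AUC without confounders, which would stand beside any inflated one. That limits the harm to the AUC. It does not protect the thresholds, which are verified from the adjusted models.

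One argument does not help the plan. Reading the totals as amounts up to the bolus does not rescue the protocolized-bolus analysis, because most would then barely vary.

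**Conclusion.** The point holds in limited form and should be corrected before analysis. Followed as written, the blood-loss part of Hypothesis III, one factor of three, has no specified variable. The protocolized-bolus regression uses covariates that either arise mostly after the outcome or are close to zero. The all-bolus regression uses totals that may include the bolus being predicted.

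The route into the adjusted models is possible, not established. If a total did enter, and were 0.5 to 1.0 SD higher in responders and independent of the index within groups, the AUC would rise by 0.04 to 0.11 from 0.70, by 0.02 to 0.06 from 0.80, and by 0.01 to 0.03 from 0.90. These figures show scale under stated assumptions and are not estimates for this trial. The coverage and timing points depend on none of them.

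**What to change.** 1. In the Aim III table and section 4.8, define each fluid, blood and vasopressor covariate, including the yes/no entries, as the exposure or cumulative amount before the start of the bolus being analysed, derived from the section 4.6.4 records. State what *total blood volume* means.
2. In the protocolized-bolus analysis, use only exposures that occurred before that bolus and omit any with no variation. Something given between induction and that bolus remains a legitimate covariate.
3. Add estimated cumulative blood loss at the start of each bolus to the Aim III covariates, and to data collection if the Data Collection Form does not already hold it.
4. State that the blood-loss part of Hypothesis III is addressed by post-incision boluses only, because surgical blood loss has not begun at the protocolized bolus.

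The cost is wording in two places, at most one extra field per bolus, and a small derivation. Fluids and vasopressors are already timed, an investigator is in the room throughout surgery, and the anesthesiologist already weighs blood loss. Care does not change.
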